2.2 TARGET POPULATION

Inclusion Criteria

- Participant is willing and able to give informed consent for the participation in the study.
- If the participant lacks capacity to consent they have a relative or friend who is a 'personal consultee' or Independent Mental Capacity Advocate who will be invited to advise on whether they believe that participation in the study would be in accordance with the values and interests of the individual.
- Male or Female, aged ≥ 65 years.
- Patient had been referred to the admission avoidance HAH service with CGA and would otherwise require hospital admission for an acute medical event. This will include patients presenting with delirium, functional decline, dependence, falls, immobility or a background of dementia presenting with physical disease.
- In the Investigator's opinion, is able and willing to comply with all trial requirements.
- Willing to allow his or her General Practitioner and consultant, if appropriate, to be notified of participation in the trial.
- English speaking.

The presence of a carer will not be a requirement for enrolment and will depend on the individual circumstances of the patient; this will be at the discretion of the clinician responsible for the patient, as is current clinical practice in each centre.

Exclusion Criteria

- Patients with acute coronary syndrome, this includes myocardial infarction and unstable angina and is characterised by cardiac chest pain and is associated with ECG changes.
- Patients presenting with symptoms which require an acute surgical assessment.
- Patients with a suspected stroke.
- Patients who are receiving end of life care as part of a palliative care pathway.
- Patients who refuse HAH service.
- Patients considered by the clinical staff to be too high risk for home based care, for example those who are physiologically unstable, who are at risk to themselves or if the carer reports HAH care who not be acceptable (in keeping with existing clinical practices for HAH).
- Patients living in a residential setting.

2.3 SAMPLE SIZE

The sample size is calculated for the primary outcome: living at home at 6 months follow up (the inverse of death or living in a residential care setting), for a 2:1 randomisation ratio with 2/3rd randomized to admission avoidance HAH with CGA and 1/3 to inpatient CGA. Several sources informed our estimate of effect size; these were one of the trials included in the IPD meta-analysis of HAH which recruited frail older people who required hospital level care (similar to the study population we plan to recruit), an audit of 750 patients who received HAH + CGA in Lanarkshire, the RCTs of CGA included in the Cochrane Review and the pooled estimate for the relative effect at 6 months obtained from the IPD Cochrane Review of HAH (3 trials, 607 participants) which was an adjusted Hazard Risk of 0.62 (95% CI 0.45 to 0.87) for mortality. Our proposed study effect estimate is based on a control group (CGA hospital) event rate at 12 months of 50% with a 10% reduction in living in a residential setting to 40% in the CGA at home group, equal to a relative risk of 0.8 which lies towards the top end of the 95% CI for the pooled estimate. We have calculated that a sample size of 1050 to achieve around 83% power at a significance level of 0.05 to detect a 10% absolute difference, assuming a control group event rate at 12 months of 50% and 6% attrition.

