2.4 RANDOMISATION AND BLINDING IN THE ANALYSIS STAGE

Following informed consent and the collection of baseline data eligible patients will be randomly allocated using a 2:1 ratio (2 admission avoidance HAH with CGA: 1 inpatient CGA) by the local member of the research team who recruited the participant. Randomisation will be performed using Sortition, Oxford University's Primary Care Clinical Trail Unit's in-house online randomisation system. Randomisation will be stratified by centre (Bradford, Newport Lanarkshire, Lothian, Fife, Royal Devon Exeter, Torfaen, North Deon, Southern Trust, Guys & St. Thomas, and Belfast), gender and by known cognitive decline.

We have opted for a 2:1 ratio as the HAH schemes have been established to ease the pressure on acute hospital beds and concern was expressed by the clinical leads that a 1:1 randomisation ratio would place unmanageable pressure on the inpatient service. This was therefore a decision related to the capacity of the service to manage patients in the two settings. This has been taken into account in our analysis plan and will not affect the estimated precision of our findings.

Due to the nature of the intervention, it is not possible to blind participants. It will also not be possible to blind research nurses who will collect outcome data as participants will know which intervention they will have received (admission avoidance HAH with CGA or inpatient admission) and are likely to discuss this with the nurse.

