4.1 PRIMARY OUTCOME

The primary outcome is living at home at 6 months follow-up. A generalised linear mixed model will be fitted to the data with living at home at 6 months as the dependent variable. The model will include intervention arm, gender, and known cognitive decline (IQCODE, the full score will be included in the model) as fixed effects, as well as stratification factors; centre as a random effect. If sites recruited only a small number of patients to the study then these will be grouped together in an 'other' category for the random effect. The

adjusted relative risk between randomised groups with 95% confidence intervals and p-value for living at home at 6 months will be derived from the model.

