11 CHANGES TO THE PROTOCOL OR PREVIOUS VERSIONS OF SAP

The primary outcome in the published protocol was originally planned to include data collected at both the 6 and 12 months' time point. However, it was decided to analyse the data collected at the two time points separately because it is now planned to potentially publish the results from the 6 months analysis before the 12 month follow-up is complete. All data that is collected at the 12 months' time point will be analysed separately from the 6 months data. In terms of the primary outcome, the analysis of both the 6 and 12 month data will be conducted as a sensitivity analysis.

The statistical analysis methods section in the published protocol states that the primary outcome of 'living at home' and other binary outcomes will be analysed using a mixed-effect logistic regression model. It has been decided to analyse the binary outcome by means of a generalised linear mixed model instead so that relative risk measures can be obtained from the model.

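### The 83% power rests on rates labelled as 12-month rates, so it is not shown to apply to the 6-month primary analysis

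*SAP*

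**What the plan says.** SAP section 2.3 opens with "The sample size is calculated for the primary outcome: living at home at 6 months follow up", and section 4.1 agrees: "The primary outcome is living at home at 6 months follow-up". The planning figures in section 2.3 carry a different time label. The section refers to a "control group (CGA hospital) event rate at 12 months of 50" per cent, reduced "to 40% in the CGA at home group, equal to a relative risk of 0.8", and it repeats the 12-month label in the power sentence, "assuming a control group event rate at 12 months of 50% and 6% attrition". That sentence states the power "to detect a 10% absolute difference", with 1050 randomised 2:1, a significance level of 0.05 and power of around 83%.

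Section 11 records that the published protocol planned a primary outcome using both 6- and 12-month data, and that "it was decided to analyse the data collected at the two time points separately". The joint 6- and 12-month model is now a sensitivity analysis (sections 6 and 11). Section 11 does not mention the sample size, and no 6-month control rate appears anywhere in the SAP.

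Two further statements belong with this point. Section 2.3 describes the planned effect as a reduction in living in a residential setting, although the same section defines the adverse event as death or residential care. Section 2.4 says of the 2:1 ratio: "This has been taken into account in our analysis plan and will not affect the estimated precision of our findings".

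**The concern.** The endpoint and the rates behind its power carry different time labels. The label appears twice, and 12-month data were once part of the primary analysis, so it could be a remnant of that plan as easily as a slip. Either way, the SAP gives no event rate for the time point at which the primary comparison is made.

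This matters because a relative risk of 0.8 and a 10-point difference are the same effect only at a 50% control rate. If fewer control patients have died or entered residential care by 6 months than by 12, the two descriptions separate, and power moves in opposite directions depending on which one is kept. A reader of a null 6-month result would take it as coming from a trial with 83% power, and the document does not show that.

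The precision sentence in section 2.4 is a smaller matter, but at a fixed total it is untrue.

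**Working it through.** **Inputs from SAP section 2.3.** Total 1050; 2:1 allocation; 6% attrition; control 50%, intervention 40%; significance level 0.05. The SAP does not state sidedness; two-sided is assumed.

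**Numbers analysed.** 1050 × 0.94 = 987, split 658 (hospital at home) and 329 (inpatient).

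**Formula.** Power = Φ[(d − 1.96 × s0) / s1], where d is the difference in event rates, s0 = √[p̄(1 − p̄)(1/329 + 1/658)], s1 = √[pC(1 − pC)/329 + pT(1 − pT)/658], and p̄ is the weighted mean rate. With continuity correction, d is reduced by (1/329 + 1/658)/2 = 0.00228.

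**The plan's own figure.** For 50% versus 40%, p̄ = 0.4333, s0 = 0.03346 and s1 = 0.03354.
- Uncorrected: (0.1000 − 0.0656)/0.03354 = 1.03, power 84.8%.
- Corrected: (0.0977 − 0.0656)/0.03354 = 0.96, power 83.1%.
- In reverse, 83% power with correction needs 329 controls, 987 in all, and 987/0.94 = 1050.

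So 1050 and 83% are right for 50% versus 40%.

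**Power at 6 months.** The control rates below are assumptions, because the SAP gives none. Same formula, no continuity correction, 658 and 329 analysed.

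| Control rate | Rate at RR 0.8 | Power at RR 0.8 | RR implied by 10 points | Power for 10 points | Difference detectable with 83% power |
|---|---|---|---|---|---|
| 50% | 40.0% | 85% | 0.80 | 85% | 9.8 points |
| 45% | 36.0% | 78% | 0.78 | 86% | 9.6 points |
| 40% | 32.0% | 70% | 0.75 | 88% | 9.4 points |
| 35% | 28.0% | 61% | 0.71 | 90% | 9.0 points |
| 30% | 24.0% | 53% | 0.67 | 93% | 8.5 points |

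RR is the relative risk of death or residential care.

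**An illustration.** If hazards were constant and led to 50% and 40% at 12 months, the 6-month rates would be 1 − √0.5 = 29.3% and 1 − √0.6 = 22.5%. That is a difference of 6.7 points, with power of about 64% (61% corrected). The constant hazard is an assumption of this check, not of the SAP.

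**Allocation.** At a fixed total of 987, with a common outcome variance, the variance under 2:1 relative to 1:1 is (1/658 + 1/329)/(4/987) = 1.125. The standard error is √1.125 = 1.061 times as large. For 50% versus 40%, uncorrected power is 84.8% under 2:1 and 88.6% under 1:1.

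**The case against.** A reader might infer that the trial lacks its stated power at 6 months. The document does not support that. The power sentence in section 2.3 is written for a 10-point absolute difference, and power for that difference rises as the control rate falls below 50%. The relative risk of 0.8 is given only as the equivalent of 50% versus 40%. Section 4.1 estimates the relative risk of living at home, where the planning effect is 60/50 = 1.2. Holding that value constant at control event rates of 45, 40, 35 and 30% gives power of 92, 96, 99 and 99.9%, though it implies differences of 11 to 14 points. The direction of any error therefore depends on a scale that the SAP does not choose for 6 months.

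The 6-month rate is also unknown. It is probably below the 12-month rate, but this is not a necessity: section 2.1.1 defines the outcome by status at the visit, and a stay in residential care can end. If the 12-month label is a slip for 6 months, the 83% stands.

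All of this holds, and it rules out a claim of lost power. It does not supply the missing basis. Section 2.3 defends the effect size on the relative scale, placing 0.8 towards the upper end of a pooled interval of 0.45 to 0.87. A 10-point difference at a 30% control rate would mean a relative risk of 0.67, a larger effect than the one defended. Nothing in the SAP says that the full 12-month difference is present by 6 months.

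On the side points, the same section defines the event correctly elsewhere, so the residential wording is a slip. The cost of 2:1 allocation is already inside the 83%, since the calculation uses that ratio; only the statement about precision is wrong.

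**Conclusion.** The concern holds as an unreconciled inconsistency, not as an arithmetic error. The 83% is correct for 50% versus 40%, but those rates are labelled 12 months while the primary analysis is at 6 months, and the change recorded in section 11 did not prompt a new justification.

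The size is a range. For control rates of 45% down to 30%, 6-month power is about 78% down to 53% if the relative risk of 0.8 carries over, and about 86% up to 93% if a 10-point difference does. These figures assume a two-sided test and 987 analysed, and make no allowance for covariate adjustment or the centre random effect. Neither end can be called the trial's power until the sponsor states a 6-month control rate and an effect scale. The precision claim in section 2.4 is wrong at a fixed total, by 12.5% in variance.

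**What to change.** In section 2.3, reconcile the time label.
- If 50% is the assumed 6-month rate, correct the label; the 83% then stands.
- If 50% is a 12-month rate, say that 83% applies to 50% versus 40% at 12 months. State the assumed 6-month control rate and the effect scale. Give 6-month power on both scales, as in the table above, with the difference detectable at 83% power (about 9.6 down to 8.5 points for control rates of 45% to 30%). Showing only the unfavourable scale would be as incomplete as the present text.

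In either case, describe the planned effect as a reduction in death or residential care, and note the outcome of this reconciliation in section 11.

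In section 2.4, replace the precision sentence with a statement that the 2:1 ratio is allowed for in the power calculation and gives a variance about 12.5% larger than 1:1 at the same total.

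The cost is SAP wording only. Enrolment, data collection and the primary model are unchanged. The downside is that the stated power may become less favourable.

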2.4 RANDOMISATION AND BLINDING IN THE ANALYSIS STAGE

Following informed consent and the collection of baseline data eligible patients will be randomly allocated using a 2:1 ratio (2 admission avoidance HAH with CGA: 1 inpatient CGA) by the local member of the research team who recruited the participant. Randomisation will be performed using Sortition, Oxford University's Primary Care Clinical Trail Unit's in-house online randomisation system. Randomisation will be stratified by centre (Bradford, Newport Lanarkshire, Lothian, Fife, Royal Devon Exeter, Torfaen, North Deon, Southern Trust, Guys & St. Thomas, and Belfast), gender and by known cognitive decline.

We have opted for a 2:1 ratio as the HAH schemes have been established to ease the pressure on acute hospital beds and concern was expressed by the clinical leads that a 1:1 randomisation ratio would place unmanageable pressure on the inpatient service. This was therefore a decision related to the capacity of the service to manage patients in the two settings. This has been taken into account in our analysis plan and will not affect the estimated precision of our findings.

Due to the nature of the intervention, it is not possible to blind participants. It will also not be possible to blind research nurses who will collect outcome data as participants will know which intervention they will have received (admission avoidance HAH with CGA or inpatient admission) and are likely to discuss this with the nurse.

3 ANALYSIS – GENERAL CONSIDERATIONS

3.1 DESCRIPTIVE STATISTICS

Frequencies (with percentages) for binary and categorical variables and means (with standard deviations), or medians (with lower and upper quartiles) for continuous variables will be presented.

3.2 CHARACTERISTICS OF PARTICIPANTS

Baseline characteristics of participants (age, gender, education, place of assessment, consent signed by consultee, presenting problem and diagnosis) and baseline outcome data; co-morbidity (Charlson index), activity of daily living (Barthel index), cognitive impairment (MoCA), cognitive status (IQCODE), health status (EQ5D), and delirium (CAM) will be summarised for both randomised groups. There will be no tests of statistical significance nor confidence intervals for differences between randomised groups on any baseline variables.

Patient throughput from screening through randomisation, follow up and analysis will be presented in a CONSORT flow chart (Appendix IV).

3.3 DEFINITION OF POPULATION FOR ANALYSIS

All data will be included in the analysis as far as possible to allow full ITT analysis. Patients will be analysed in the groups they were allocated, irrespective of whether they received that intervention or not.

3.4 POOLING OF INVESTIGATIONAL SITES

Analysis will not be pooled as the primary and secondary analysis sufficiently account for the different centres.

3.5 DATA MONITORING COMMITTEE AND INTERIM ANALYSES

The trial is of a method of management rather than a medicinal product and it is not anticipated that the trial will be terminated unless on the advice of the Data Monitoring Committee (DMC) in the case of a series of Suspected Unexpected Serious Adverse Reactions (SUSARs).

No interim analysis was planned in the protocol.

A separate document details the data/information which will be presented in the DMC report (located: K:\HB_O\CGA\STATS\3. TSC and DMC\DMC\DMC report template)

4 PRIMARY ANALYSIS

The primary objective is to test the effectiveness of admission avoidance HAH with CGA compared with CGA and investigate the generalizability of CGA in settings where health and social care provision vary.

4.1 PRIMARY OUTCOME

The primary outcome is living at home at 6 months follow-up. A generalised linear mixed model will be fitted to the data with living at home at 6 months as the dependent variable. The model will include intervention arm, gender, and known cognitive decline (IQCODE, the full score will be included in the model) as fixed effects, as well as stratification factors; centre as a random effect. If sites recruited only a small number of patients to the study then these will be grouped together in an 'other' category for the random effect. The

adjusted relative risk between randomised groups with 95% confidence intervals and p-value for living at home at 6 months will be derived from the model.

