6 SENSITIVITY ANALYSIS

Sensitivity analysis will be conducted with respect to the primary outcome only (unless explicitly stated) and will explore the sensitivity of results to different assumptions regarding missing data, outliers and departure from randomisation policy.

- 1) The generalised linear mixed model assumes that the data is missing at random (MAR). A logistic regression analysis will be conducted to investigate factors at baseline (if any) that are predictive of non-response. If any factors are associated with non-response, the generalised linear mixed model in the primary analysis will be re-run with these factors included as fixed covariates in the model.
- 2) Some patients might have missing data for the 'living at home' at 6 months outcome due to missing place of assessment and/or death status. These patients will have their missing place of assessment and/or death status replaced with each of the alternatives for these variables:
 - i) Living at home and alive
 - ii) Not living at home and alive
 - iii) Dead

The 'living at home' at 6 months outcome will be re-derived, and the generalised linear mixed model in the primary analysis in section 4.1 will be re-conducted with each of these replacements to the outcome.

- 3) Some patients might have missing data for the 'living at home' at 6 months outcome due to missing place of assessment and/or death status. Patients with missing 'living at home' at 6 months outcome will have their missing place of assessment and/or missing death status imputed using multiple imputation (MI). A fully inclusive MI will be conducted with; gender, age, education, place of baseline assessment, if consent signed by 'consultee', and other factors expected to relate to the main outcome (i.e. practice, presenting problems at baseline, diagnosis of delirium at baseline) as covariates. The primary outcome will then be re-derived using the same method as in section 2.1.1. The generalised linear mixed model in the primary analysis in section 4.1 will be repeated for the imputed dataset and the results compared to those from the primary analysis.

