8 ADDITIONAL EXPLORATORY ANALYSIS

The following analysis has been planned as exploratory only.

1) Charlson Comorbidity index

The Charlson index [6] assesses whether a patient will live long enough to benefit from a specific screening measure or medical intervention. The Charlson index is used to derive a variable for Charlson score and Charlson probability, and is assessed by baseline and 6 months follow-up. The Charlson index is a 16 item questionnaire (variables *ccicon1 – ccicon16*) with questions on if the patient has a particular comorbidity or not. To obtain the Charlson Comorbidity Index score add up the score from each question in the index, add an extra point if the patient is aged between 50 and 59, add 2 extra points if the patient is aged between 60 and 69, add 3 extra points if the patient is aged between 70 and 79, add 4 extra points if the patient is 80+, and add 0 extra points if the patient is less than 50. To obtain Charlson probability (10-year survival):

$$\text{Charlson probability} = 0.983^{CII*0.9}$$

Where CII = Charlson Comorbidity Index score.

The mean, standard deviation, median, minimum value, and maximum value of the Charlson comorbidity score and Charlson probability will be presented at each time point and in each randomised group. No statistical tests for differences will be performed.

2) Clinical Diagnosis of Delirium at Baseline

Delirium is measured at baseline, 3 days, 5 days, and 1 month follow-up using the CAM questionnaire. A clinical diagnosis of delirium is also collected at baseline. The frequencies and percentages of patients that have a clinical diagnosis of delirium at baseline will be summarised in a two-way table against the frequencies and percentage of patients that were tested positive for delirium by the CAM questionnaire. This is exploratory only to see how these two methods compare. No formal analysis will be conducted.

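### The primary model is valid, but adding baseline predictors already collected (age, Barthel, Charlson, delirium) would be a cheap gain in power whose size depends on an unknown R²

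*SAP*

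**What the plan says.** SAP section 4.1 fits a generalised linear mixed model to living at home at 6 months and takes an adjusted relative risk from it. On covariates it says: "The model will include intervention arm, gender, and known cognitive decline (IQCODE, the full score will be included in the model) as fixed effects". Centre enters as a random effect. These are the three factors by which section 2.4 stratifies randomisation, with IQCODE as the full score.

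Section 3.2 lists age among the baseline characteristics, and among the baseline outcome data it lists "co-morbidity (Charlson index), activity of daily living (Barthel index), cognitive impairment (MoCA), cognitive status (IQCODE), health status (EQ5D), and delirium (CAM". Appendix II confirms that Barthel, Charlson and CAM are collected at baseline. None of these is in the primary model.

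Two other sections bear on whether they are prognostic:

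- Section 6 item 3 (multiple imputation) lists gender, age, education, place of baseline assessment and consultee consent, and then "other factors expected to relate to the main outcome (i.e. practice, presenting problems at baseline, diagnosis of delirium at baseline) as covariates".
- Section 8 item 1 says that the Charlson index "assesses whether a patient will live long enough to benefit from a specific screening measure or medical intervention". It adds points for age and converts the score to a 10-year survival probability.

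Extra covariates can reach the primary model only through section 6 item 1, a sensitivity analysis, and only if they predict non-response.

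**The concern.** The primary outcome combines survival with staying out of residential care. It has no baseline value to adjust for, because section 2.2 excludes patients who live in a residential setting. Prognostic covariates are the available substitute. The SAP collects several, expects at least some of them to relate to the outcome, and uses them for imputation or description but not in the primary model. A variable that predicts the outcome strongly but does not predict missingness would never enter.

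Three things are at stake.

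- **Precision.** Explaining more of the outcome variation narrows the confidence interval for the relative risk without recruiting anyone.
- **Chance imbalance.** In an open trial, adjustment for age or dependency is credible only if it is fixed beforehand.
- **Missing data.** Section 4.2 relies on data missing at random. With one time point, that can hold only conditionally on the covariates in the model, and a richer set makes it more plausible.

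**Working it through.** **Inputs from SAP section 2.3**

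- Size and power: "We have calculated that a sample size of 1050 to achieve around 83% power at a significance level of 0.05". Sidedness is not stated; two-sided is assumed.
- Effect and attrition: "to detect a 10% absolute difference, assuming a control group event rate at 12 months of 50% and 6% attrition", so 1050 × 0.94 = 987 evaluable.
- Intervention event rate: "with a 10% reduction in living in a residential setting to 40% in the CGA at home group".
- Allocation: "for a 2:1 randomisation ratio with 2/3rd randomized to admission avoidance HAH with CGA and 1/3 to inpatient CGA", so 658 hospital at home and 329 inpatient.
- Added R² of the four covariates beyond gender, IQCODE and centre: not in the document. Assumed range 0.02 to 0.20.

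**Step 1: reproduce the stated power**

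- Pooled rate = (0.50 × 329 + 0.40 × 658)/987 = 0.4333
- SE under the null = √[0.4333 × 0.5667 × (1/329 + 1/658)] = 0.03346
- SE under the alternative = √[0.25/329 + 0.24/658] = 0.03354
- Continuity correction = (1/329 + 1/658)/2 = 0.00228

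Power with the correction = Φ[(0.10 − 0.00228 − 1.96 × 0.03346)/0.03354] = Φ(0.958) = 83.1%. Without the correction it is Φ(1.026) = 84.8%. Solving for sample size at 83% power with the correction gives 329 controls, 987 in total, and 987/0.94 = 1050. The stated design is reproduced, and it is an unadjusted comparison of two proportions.

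**Step 2: add prognostic covariates**

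An added R² multiplies the outcome variance by (1 − R²), so both standard errors are multiplied by f = √(1 − R²). For R² = 0.10, f = 0.9487 and power = Φ[(0.10 − 0.00228 − 1.96 × 0.03174)/0.03181] = Φ(1.116) = 86.8%.

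| Assumed added R² | Power, with correction | Power, without correction | Gain (points) | Equivalent evaluable sample, 987/(1 − R²) |
|---|---|---|---|---|
| 0 | 83.1% | 84.8% | – | 987 |
| 0.02 | 83.8% | 85.5% | about 0.7 | 1007 |
| 0.05 | 85.0% | 86.5% | about 2 | 1039 |
| 0.10 | 86.8% | 88.3% | about 3.5 | 1097 |
| 0.15 | 88.6% | 90.0% | about 5 | 1161 |
| 0.20 | 90.4% | 91.6% | about 7 | 1234 |

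**Step 3: cross-check on the relative-risk scale**

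For each setting, 4000 trials were simulated with 329 against 658 patients and 50% against 60% living at home. A Poisson log-link model with robust variance was fitted twice. The first fit had one covariate standing in for those already in the model, and the second added four more.

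| Approximate added R² | Power, base model | Power, four covariates added | Gain (points) |
|---|---|---|---|
| 0.02 | 84.4% | 85.1% | 0.7 |
| 0.05 | 85.1% | 86.6% | 1.5 |
| 0.09 | 85.1% | 88.3% | 3.2 |
| 0.16 | 84.0% | 89.4% | 5.4 |
| 0.22 | 84.6% | 91.7% | 7.1 |

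The gains agree with the formula. Centre effects were not simulated.

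**The case against.** The strongest reply is that nothing here is wrong. The model contains every stratification factor, the comparison is valid, and the 83% was calculated without covariates, so the planned analysis does not fall short of it. That stands. A reader might infer that the primary analysis is flawed or the trial underpowered because of the omission; the document supports neither.

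A reader might also infer that the SAP gives up several points of power as a matter of fact. It gives no R², AUC or outcome association. Below an added R² of 0.05 the gain is under 2 points. A gain of several points needs 0.10 or more on top of what gender, IQCODE and centre explain.

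Nor does the SAP treat all four variables as predictors of this outcome:

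- Barthel is never linked to it.
- Charlson has only a general description as a survival measure. Death is a component of the outcome, but the SAP does not draw the link.
- Section 6 names a baseline diagnosis of delirium without saying whether it means CAM or the clinical diagnosis. Section 8 item 2 treats these as separate measures.

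There is also no internal contradiction. The delirium, MoCA and Barthel models adjust for the baseline of the same measure, which the primary outcome lacks. The models for mortality, residential care and readmission use the same covariates as the primary model. An imputation model broader than the analysis model is normal practice. The covariate set may come from the protocol, which is not at hand, so the lack of a stated reason is not held against the SAP.

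What survives is narrower: at least baseline delirium, and by its wording age, is expected by the SAP itself to matter. The data are in hand and adjustment costs little.

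**Conclusion.** A worthwhile, low-cost improvement to section 4.1, not a correction. Under the design figures of section 2.3, prespecified adjustment for the four variables would raise power from about 83% by roughly 0.7 points at an added R² of 0.02, 2 at 0.05, 3.5 at 0.10, 5 at 0.15 and 7 at 0.20.

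These figures rest on the assumed R², a two-sided 0.05 level, 987 evaluable patients split 2:1, and event rates of 50% and 40%. Section 2.3 states the 50% for 12 months while the primary outcome is at 6 months; it is used here as given. The case is firmest for delirium and age, reasonable for Charlson, and a matter of judgement for Barthel.

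**What to change.** Before the analysis, amend section 4.1 as follows.

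- **Covariates.** Add baseline age, Barthel index, the Charlson comorbidity items without their age points (age enters separately), and one named baseline delirium variable, either CAM or the clinical diagnosis. Keep gender, IQCODE and centre.
- **Missing baseline values.** Fill them by a rule that ignores treatment arm, for example the overall mean or most frequent category, so that no patient is dropped. The SAP does not say how much baseline data is missing, so the rule should not assume that it is little.
- **Convergence.** If the relative-risk mixed model does not converge, use a Poisson log-link model with robust errors that retains centre, or standardise from a logistic model that retains centre. Fix the order of these beforehand.
- **Present model.** Report it as a sensitivity analysis.

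Presenting problem is also named in section 6 and could be considered, but the SAP does not define its categories, so it would first need a coding rule.

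The cost is SAP wording and a few lines of code on data already collected. The downsides are a somewhat higher risk of non-convergence and a small return if the covariates add little.
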